7.2. Questionnaire

The following questionnaire will be completed by each participant after the crossover study period during which the PLGS system was used. The procedures for administration are described in the study procedures manual.

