9.2. Participant Withdrawal

Participation in the study is voluntary, and a participant may withdraw at any time. For participants who withdraw, their data will be used up until the time of withdrawal.

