129 Total percentage of time PLGS and CGM is used per week will be calculated by dividing the total number of hours of PLGS readings by the maximum possible number of hours within the study period visit dates described above. Number of days of PLGS and CGM use per week is calculated as the count

132 of days during the week where there was at least one PLGS/CGM reading. Data from both study periods
133 will be included in this analysis. No missing data will be imputed.

134

135 **Hypoglycemic Events**

136 A CGM-measured hypoglycemic event will be defined as:

- 137 • at least 2 sensor values < 54 mg/dl
- 138 • that are 15 or more minutes apart
- 139 • no intervening values > 54 mg/dl
- 140 • Event ends when:
 - 141 ➤ at least 2 sensor values > 70 mg/dl
 - 142 ➤ that are 30 or more minutes apart
 - 143 ➤ no intervening values < 70 mg/dl
- 144 • Participant becomes eligible for a new event as soon as the above criteria for ending the previous
145 event have been met.

146

147 **5. Description of Statistical Methods**

148

149 **5.1 General Approach**

150 All analyses will compare the 3-week period of PLGS to the 3-week period of SAP and will follow the
151 intention-to-treat principle with each period analyzed according to the treatment assigned by
152 randomization regardless of actual PLGS or SAP utilization. All participants who have at least one
153 CGM reading in each 3-week period will be analyzed for the primary and secondary outcomes. All p-
154 values will be two-sided.

155

156 Standard residual diagnostics will be performed for all analyses. If values are highly skewed, then a
157 transformation or nonparametric methods will be used instead. Previous experience suggests that a
158 transformation may be necessary for the hypoglycemic and hyperglycemic outcomes. We do not expect
159 that a transformation will be necessary for some overall glucose control metrics (such as mean glucose).

160

161 **5.2 Analysis Cohorts**

- 162 • All randomized participants who have at least one CGM reading in both 3-week periods will be
163 analyzed for the Intention-to-Treat (ITT) Analysis with each day included in the treatment group
164 assigned by randomization.
- 165 • Safety outcomes will be reported for all enrolled participants, irrespective of whether the study was
166 completed.
- 167 • A per-protocol analysis will be restricted to participants with ≥ 200 hours of CGM data in each 3-

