168 week period. This analysis will only involve the primary outcome, and will only be done if at least
169 10% of subjects are excluded based on this criterion.

170

171 **6. Analysis of the Primary Efficacy Endpoint**

172

173 **6.1 Included Subjects**

174 As noted in section 5.2, the primary analysis for this study will include all randomized subjects with at
175 least one CGM sensor reading in each of the two treatment periods. No additional minimum amount of
176 CGM use is required otherwise.

177

178 **6.2 Missing Data**

179 There will be no imputation of missing CGM data for the primary analysis in this study.

180

181 **6.3 Statistical Methods**

182 Mean \pm SD (standard deviation) or summary statistics appropriate to the distribution will be reported for
183 % time below 70 mg/dL for each treatment arm. A repeated measures regression model with an
184 unstructured covariance structure will be fit for percent time below 70 mg/dL to compare the two
185 treatments. The model will adjust for period as a covariate.

186

187 Residual values from the above model will be examined for an approximately normal distribution. It is
188 likely that the residuals themselves will have a skewed distribution, but that the paired differences from
189 the same subject may follow an approximate bell-shaped curve. However, if the paired differences have
190 a skewed distribution, then an appropriate transformation or a nonparametric analysis based on ranks
191 will be performed. Significance will be assessed at the 5% level.

192

193 A carryover effect is not expected, but it will be assessed with a separate model built with the inclusion
194 of a period by treatment interaction. However, the study is not expected to have sufficient power in
195 making definitive conclusions about the period by treatment interaction.

196

197 **7. Analysis of the Secondary Endpoints**

198 The same subjects will be included as in the primary analysis. Missing data will not be imputed for any
199 of the secondary analyses in this study.

200

201 **7.1 Statistical Methods**

202 For all secondary outcomes, summary statistics appropriate to the distribution will be tabulated by
203 treatment group. Analysis of all secondary endpoints will parallel the primary analysis. A ranked normal
204 score transformation will be applied to all highly skewed secondary outcomes.

205

206 **7.2 Secondary Analyses by Time of Day**

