424 **14. Exploratory Analyses**

425 No additional exploratory analyses are planned.

431

432 15. Additional Analyses

433 The following outcomes will be tabulated separately over a 24-hour period, daytime, and nighttime
434 where applicable:

- 435 • Insulin delivery per treatment group, including total insulin units per day, basal insulin units
436 per day, and bolus insulin units per day.
- 437 • PLGS group only: Frequency of insulin suspension events and duration of events per subject-
438 day, including individual suspensions and cumulative suspension time
- 439 • PLGS group only: CGM glucose nadir during suspension events and peak within 2 hours
440 after events.

441

442 Mean \pm SD or summary statistics appropriate to the distribution will be reported for each of these
443 outcomes. Insulin delivery will be compared between treatments using the same model described above
444 for the primary outcome.

445

446 Total basal insulin is recorded as an hourly cumulative running total of the amount of basal insulin
447 delivered for each day. Total basal insulin will be calculated by a summation of the increments between
448 the cumulative counts for each day, not including days where the insulin pump was reset or days where
449 a time change caused basal readings to overlap. Total bolus will be calculated by summing all non-
450 missing bolus delivery amounts recorded by the insulin pump for each period.

451

452 App-Based Monitoring and Intervention Questionnaire

453 Visits in which participant took carbs or insulin to correct blood glucose in response to a commercially-
454 available CGM monitoring app will be tabulated by treatment group. The questions are answered at
455 every visit past the first study period's initiation visit, and include any carbs or insulin taken since the
456 last visit or contact. Responses are a binary yes/no. Summary statistics tabulated will include number
457 and percentage of a) participants taking carbs and b) participants taking insulin at each visit/contact. The
458 analysis cohort for all of these additional analyses are the same as the primary analysis. Data from both
459 study periods (defined in section 4.3) will be included in this analysis. No missing data will be imputed.

460

461 System Usability Questionnaire

462 This 10-item questionnaire is given at the end of every participant's PLGS study period to determine
463 system usability of the PLGS feature:

464

465

Question

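### SAP 15 requires CGM data in both periods for suspension and nadir/peak outcomes that exist only under PLGS, so PLGS-first participants who leave before any Period 2 reading are dropped while comparable control-first leavers are kept

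*SAP*

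**What the plan says.** In this note SAP means the statistical analysis plan; the sensor-augmented pump period is called the control period.

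SAP 15 lists insulin delivery by treatment, then two outcomes confined to one period: "PLGS group only: Frequency of insulin suspension events and duration of events" and "PLGS group only: CGM glucose nadir during suspension events and peak within 2 hours". The app-monitoring questionnaire follows. Its closing paragraph says that the "analysis cohort for all of these additional analyses are the same as the primary analysis".

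SAP 6.1 defines the primary cohort as randomized participants with at "least one CGM sensor reading in each of the two treatment periods" and sets no further minimum. SAP 5.2 agrees.

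The System Usability Questionnaire comes after the cohort sentence, under its own heading. That text says "This 10-item questionnaire is given at the end of every participant's PLGS study period to determine" usability, and names no cohort.

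Two protocol passages bear on this. Protocol 9.2 says: "For participants who withdraw, their data will be used up until the time of withdrawal". Protocol 10.5.1, by contrast, states a general rule that those with a CGM reading in each period are analyzed.

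**The concern.** Requiring data in both periods makes sense where each participant contributes a PLGS-minus-control contrast. SAP 5.1 ties the requirement to the primary and secondary outcomes for that reason. Suspension, nadir and peak outcomes have no control-period counterpart, so the requirement only discards PLGS data already collected. What it discards depends on randomized order, because a PLGS-first participant still has to produce a reading in a later period and a control-first participant does not.

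These tables matter for describing the device. Protocol 1.4.1 names hyperglycemia after extended suspension as the main risk of PLGS, and Protocol 1.1 says the data are meant to support a premarket approval application. The account of suspensions should not omit exposed participants because of missing data from a period in which suspensions cannot occur.

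**Working it through.** The plan gives no figure for this cohort, so there is none to reproduce. The check is a reading of the rule by sequence, followed by a scenario count.

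**Inputs**
- Cohort rule: SAP 15, pointing to SAP 5.2 and 6.1.
- Two sequences, allocated 1:1: Protocol Summary and Protocol 5.6.
- Participants who stop the device are encouraged to stay to the final visit (Protocol 8.6.1), and periods are analyzed as assigned whatever the actual use (SAP 5.1).
- Group A completes the usability form at the visit that ends Period 1 and starts Period 2 (Protocol 5.6.1). Group B completes it at the final visit (Protocol 5.6.2).
- The Period 2 data window opens when the participant leaves that Period 2 initiation visit, or the day after if the time is unknown (SAP 4.3).
- About 100 randomized, at least 90 completing with usable data: Protocol 2.1.

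**Step 1. The rule applied by sequence**

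| Case | PLGS-first | Control-first |
|---|---|---|
| 1. Leaves the study during PLGS after at least one PLGS-period reading | Excluded; no Period 2 reading | Kept, given a control-period reading |
| 2. Stops PLGS, stays, has a reading in each period | Kept | Kept |
| 3. Finishes PLGS, then has no later reading | Excluded, with a full period of suspension data | Kept; PLGS is the last period |
| 4. Leaves during the control period | Kept with at least one control-period reading | No PLGS data to lose |

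The asymmetry lies in cases 1 and 3. It follows from the wording and needs no numerical assumption. Case 2 shows that stopping the device is not the trigger.

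**Step 2. Usability**

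The form is scheduled only at the end of the PLGS period, so a case 1 leaver has no scheduled score in either sequence. If the cohort rule reaches this scale, the people affected are mainly in case 3: PLGS-first participants who finish PLGS, complete the form and then leave. Their score exists before a Period 2 reading is possible.

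**Step 3. How many participants**

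Planned losses: 100 − 90 = 10. Split evenly over two sequences and two periods, PLGS-first losses in Period 1 are 10/4 = 2.5, so about 2 to 3. If losses split evenly by sequence and all PLGS-first losses fall in Period 1, the count is 10/2 = 5 of 50.

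**Step 4. Size of the effect on a mean (scenario)**

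Assume 50 per sequence, k leavers per sequence during PLGS, each with at least one reading in every period entered, and no other losses. Let leavers differ from the rest by D units of the outcome. The documents give neither k nor D.

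- Current rule: N = 100 − k; the mean is shifted by kD/(100 − k).
- All with PLGS-period data: N = 100; the mean is shifted by 2kD/100.
- Apparent gap between sequences under the current rule: kD/50, because leavers remain in one sequence only.

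With D = 20:

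| k | N, current rule | Shift, current rule | Shift, all PLGS data | Difference | Sequence gap |
|---|---|---|---|---|---|
| 1 | 99 | 20/99 = 0.20 | 0.40 | 0.20 | 20/50 = 0.4 |
| 2 | 98 | 40/98 = 0.41 | 0.80 | 0.39 | 40/50 = 0.8 |
| 5 | 95 | 100/95 = 1.05 | 2.00 | 0.95 | 100/50 = 2.0 |

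**The case against.** The strongest defence is that a single cohort across tables is a legitimate choice and that SAP 15 follows Protocol 10.5.1. The PLGS-only outcomes are tabulated without a treatment test. Participants who leave early remain visible elsewhere: SAP 8.3 tabulates safety outcomes for all subjects, including withdrawals, and SAP 9.2 tabulates device issues by treatment and provides flow charts of dropouts. All of this stands and limits the consequence. It does not supply a reason for the control-period requirement on outcomes that have no control value.

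It also stands that Protocol 9.2 is a general statement and does not set each analysis cohort. Its tension with the both-periods rule calls for alignment; it does not by itself show that SAP 15 is wrong.

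Three stronger readings are tempting, and the documents do not support them:

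- A reader might infer that anyone who gives up PLGS disappears if randomized to it first. Under Protocol 8.6.1 and SAP 5.1 and 6.1, a participant who stops the device, stays, and has one reading in each period is included.
- A reader might infer that usability scores are certainly restricted and therefore inflated. The cohort sentence precedes the usability heading, so its reach is ambiguous, and those who leave mid-period have no scheduled score under either cohort.
- A reader might see a contradiction with Protocol 7.2, which says "The following questionnaire will be completed by each participant after the crossover study period during which the PLGS system was used". That governs who fills in the form, not who is analyzed.

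**Conclusion.** The concern holds for suspension frequency and duration and for the nadir and peak outcomes: the both-periods rule is unnecessary there and acts differently by sequence. For the System Usability Scale the finding is only that the cohort is unstated and needs stating.

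The consequence is modest. Only descriptive tables are touched, and the primary result is unaffected. Perhaps 2 to 5 participants are involved, assuming about 10 losses among 100 split evenly by sequence. In the scenario with D = 20, one or two leavers per sequence move the pooled mean by 0.2 to 0.4 units, and five move it by 0.95. It is plausible that people who leave had more trouble with the device, but nothing in the documents shows it, so the direction of any bias is open.

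**What to change.** - In SAP 15, keep the two-period cohort for the insulin comparison between treatments.
- Define suspension frequency and duration, nadir and peak on all randomized participants with any PLGS-period data.
- Under the System Usability heading, name the cohort: all randomized participants with a completed questionnaire, whether or not they have data in the other period.
- Report the numbers missing from each of these tables by sequence.
- Align the general both-periods sentence in Protocol 10.5.1, so that it does not override the new SAP text and is consistent with Protocol 9.2.

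The cost is a few sentences and no new data collection. The PLGS-only tables will have a slightly different N from the primary analysis, which a footnote can explain.
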